8.6.2. Clinical Laboratory Parameters

All clinical laboratory parameters, their changes from baseline, and percentage changes from baseline will be listed, as applicable; any value outside the clinical reference range will be flagged. Separate listings will be provided for any parameter for which there is any individual subject value outside the respective clinical reference range.

Summary tables by timepoint will be provided for clinical chemistry, hematology, and urinalysis parameters, with changes from baseline and percentage changes from baseline, as applicable.

Values recorded as $< x$, $\leq x$, $> x$, or $\geq x$ will be displayed in the listings as recorded. For the derivation of listing flags and calculation of summary statistics, $< x$ and $\leq x$ values will be set to 0, whereas $> x$ and $\geq x$ values will be set to x.

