8.1.4. Definitions of Baseline, Change from Baseline, and Percentage Change from Baseline

The baseline will be defined as the last value recorded prior to dosing. If the date/time of the value is incomplete or missing, it will be excluded from the baseline calculation, unless the incomplete date/time indicates the value was recorded prior to dosing.

Individual changes from baseline will be calculated by subtracting the individual subject's baseline value from the value at the postdose timepoint.

Individual percentage changes from baseline will be calculated by subtracting the individual subject's baseline value from the value at the postdose timepoint, then dividing this calculated value by the individual subject's baseline value and multiplying by 100.

The summary statistics for change from baseline and percentage changes from baseline will be derived from individual subjects' values (eg, mean change from baseline will be the mean of the individual changes from baseline for all subjects, rather than difference between the mean value at the postdose timepoint and mean value at baseline).

See [Section 8.1.3](#) for more detail on handling repeat and unscheduled readings in the calculations.

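### Laboratory range flags and percentage changes are computed after censored results are replaced by 0 or x, so a flag can contradict the recorded result and any censored postdose value counts as -100%

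*SAP*

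**What the plan says.** SAP 8.6.2 keeps censored laboratory results visible: they "will be displayed in the listings as recorded". It then defines a numerical substitute with a stated scope: "For the derivation of listing flags and calculation of summary statistics". Within that scope, `<x` and `<=x` "values will be set to 0, whereas" `>x` and `>=x` become x.

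The same section uses the substituted numbers in two ways. In the listings, "any value outside the clinical reference range will be flagged", and any parameter with at least one out-of-range value gets its own separate listing. For the tables: "Summary tables by timepoint will be provided for clinical chemistry, hematology, and urinalysis parameters, with changes from baseline and percentage changes from baseline, as applicable".

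SAP 8.1.4 takes the difference from baseline, "then dividing this calculated value by the individual subject's baseline value and multiplying by 100". It adds: "The summary statistics for change from baseline and percentage changes from baseline will be derived from individual subjects' values". Neither section says what happens when the substituted baseline is 0, and neither exempts range flags from the substitution.

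**The concern.** A range flag answers a yes/no question, and the recorded inequality often settles it outright. If the inequality is first replaced by one number, information the laboratory supplied is lost and the flag can be wrong or falsely certain. Flags also decide which parameters get the separate out-of-range listing, so a wrong flag affects what a reader is shown.

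A ratio is very sensitive to a substituted 0. In the numerator's postdose term, 0 always means a complete fall. In the denominator it has no defined result. About 14 subjects are planned, and Protocol Appendix 8 schedules laboratory evaluations after the first dose only on Day 8 and Day 11. A single artificial -100% would therefore be visible in a mean.

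The scope wording is also narrow. SAP 8.1 defines a broad set of calculations that includes baseline derivation and percentage change, whereas 8.6.2 names only flags and summary statistics. Whether individual listed changes use the 0 is implied through 8.1.4, not stated.

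**Working it through.** The plan gives no figure of its own to reproduce on this point.

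**Inputs**
- Substitution rule and flag rule: SAP 8.6.2. The flag is low if value < L and high if value > U, for reference range L to U.
- Percentage change = 100 × (postdose − baseline) / baseline: SAP 8.1.4.
- About 14 enrolled and about 12 completing: SAP 5.
- Reporting limits x, reference ranges and baseline values: not in the documents. All those below are assumptions for illustration.

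**Step 1: flags**

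| Recorded | Assumed range | Value used | Flag under SAP | What the record allows |
|---|---|---|---|---|
| `<0.3` | 0.2–1.2 | 0 | low | low or normal |
| `<=0.2` | 0.2–1.2 | 0 | low | low, or 0.2 itself (normal) |
| `<5` | 0–3 | 0 | none | normal or high |
| `>1.030` | 1.005–1.030 | 1.030 | none | high only |
| `<0.2` | 0.2–1.2 | 0 | low | low only (agrees) |
| `<0.1` | 0.2–1.2 | 0 | low | low only (agrees) |
| `<5` | 0–40 | 0 | none | normal only (agrees) |

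The rule is right when x is at or below the lower limit for `<x`, and when the lower limit is 0 and x does not exceed the upper limit. The first three rows give an answer that the record does not establish. The fourth is plainly wrong.

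**Step 2: censored postdose value, quantified baseline b > 0**

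100 × (0 − b) / b = −100% for every b and every x.
- b = 0.3, postdose `<0.2`: the mild end of the compatible range is 100 × (0.2 − 0.3)/0.3 = −33%. The rule gives −100%.
- b = 0.25, postdose `<0.2`: the mild end is 100 × (0.2 − 0.25)/0.25 = −20%. The rule still gives −100%.

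Effect of that one subject on the mean, if the others show no change:

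| | n = 14 | n = 12 |
|---|---|---|
| Rule, −100% | −100/14 = −7.1 | −100/12 = −8.3 |
| Mild end, b = 0.3 | −33.3/14 = −2.4 | −33.3/12 = −2.8 |
| Mild end, b = 0.25 | −20/14 = −1.4 | −20/12 = −1.7 |

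For b = 0.3 the overstatement of the fall is therefore somewhere between 0 and 66.7/14 = 4.8 points at n = 14.

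**Step 3: censored baseline**

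100 × (postdose − 0)/0 is undefined for any postdose value, including 0/0 when both are censored. The absolute change is defined but sits at one extreme. Baseline `<0.2` then 0.4 counts as +0.4, while the record allows anything above +0.2 up to +0.4.

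**Step 4: would another substitute settle it?**

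| Case (x = 0.2) | 0 | x/2 | x |
|---|---|---|---|
| Baseline 0.4, postdose `<0.2` | −100% | −75% | −50% |
| Baseline `<0.2`, postdose 0.4 | undefined | +300% | +100% |

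The answer follows the chosen substitute. That argues for not calculating the percentage, more than for choosing a different number.

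**The case against.** The strongest reply is that setting `<x` to 0 is an ordinary prespecified convention. It matches SAP 8.5.2, which also sets concentrations below the quantification limit to 0 for summaries. A reader might infer that 0 is an error and that x should replace it, as the SAP does at the upper end. The documents do not support that. For a censored baseline, 0 reports the largest rise compatible with the record and x reports the smallest: +0.2 in the `<0.2` to 0.4 example. Protocol 1.4.1.2 lists increased liver enzymes among the known risks, so understating rises is a real cost of using x. This objection stands.

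A reader might also infer that losing subjects with a censored baseline from the percentage summary is itself the defect. It cannot be cured, since a percentage of an unknown baseline is not available. The qualifier that closes the SAP sentence on summary tables may already permit omission, though the SAP does not say so. The separate TFL shells, which are not available here, may say more. On its own, this part is only missing detail.

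The flag errors need particular alignments of reporting and reference limits, and nothing in the documents shows that they occur. Listings keep the recorded result beside any flag. Protocol 7.2.2 has the investigator review all laboratory data. SAP 8.6.6 plans no inference on safety. These points limit the consequence. None of them makes a flag correct when it contradicts the recorded inequality.

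**Conclusion.** The point holds as a minor improvement. The percentage-change results follow from SAP 8.6.2 and 8.1.4 by arithmetic and do not depend on the laboratory's limits: -100% for a censored postdose value with a quantified baseline, and undefined for a censored baseline. The flag errors are conditional. They arise when x exceeds a positive lower limit for `<x`, equals it for `<=x`, exceeds the upper limit for `<x`, or equals the upper limit for `>x`.

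The illustrative size is -7.1 points on a mean of 14 from one result, against as little as -2.4. It rests on an assumed baseline of 0.3, an assumed limit of 0.2 and no change in the other subjects. It is a possible effect, not an expected one, because frequency cannot be judged without reporting limits and reference ranges.

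A reader might go further and conclude that the trial's safety conclusions or its monitoring of subjects are compromised. The documents do not support this. The effect is confined to descriptive tables and listing flags for a secondary endpoint. Clinical review is not stated to use the substituted values, and the primary pharmacokinetic analysis does not use this rule.

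**What to change.** In SAP 8.6.2, remove listing flags from the scope of the substitution and derive them from the recorded inequality:
- `<x`: low only if x is at or below the lower limit.
- `<=x`: low only if x is below the lower limit.
- `>x`: high if x is at or above the upper limit.
- `>=x`: high only if x is above the upper limit.
- Otherwise: mark as indeterminate. The SAP may add that no mark is needed where every value compatible with the record is in range, such as `<5` with a range of 0–40.

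In SAP 8.6.2 or 8.1.4, state that percentage change is not calculated when the baseline or the postdose value is censored, in listings and tables alike. Show the number of censored values beside each summary.

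The substitution of 0 for summaries of values and absolute changes can stay as a declared convention.

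The cost is a few sentences, a small programming change, an extra flag category and an extra count. Percentage summaries will rest on fewer subjects wherever results are censored, and those left out will tend to be the ones with low values. That is why the count must appear with the summary.

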8.6.3. Vital Signs Parameters

All vital signs parameters, their changes from baseline, and percentage changes from baseline, will be listed, as applicable; any value outside the clinical reference range will be flagged.

Summary tables by timepoint will be provided for all vital signs parameters, with changes from baseline and percentage changes from baseline, as applicable.

8.6.4. 12-lead Electrocardiogram Parameters

All 12-lead ECG parameters will be listed, as applicable; any value outside the clinical reference range will be flagged.

Summary tables by timepoint will be provided for all 12-lead ECG parameters.

An outlier analysis will be performed for QT interval corrected for heart rate using Fridericia's formula (QTcF). The analysis will include all individual original, repeat, and unscheduled postdose values.

The maximum postdose values will be summarized by treatment according to the following categories:

- ≤ 450 ms
- >450 and ≤ 480 ms (all instances flagged in the listing)
- >480 and ≤ 500 ms (all instances flagged in the listing)
- >500 ms (all instances flagged in the listing)

The maximum increases from baseline will be summarized by treatment according to the following categories:

- ≤ 30 ms
- >30 and ≤ 60 ms (all instances flagged in the listing)
- >60 ms (all instances flagged in the listing)

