Appendix 8: Schedule of Assessments

18 May 2022 Page 67 of 69

	Screening	Check- in	Sotora	sib (Day 1	l) and On Alone	neprazole (Day	y 4-8)		rasib in Comb	oination with
Study Procedures	Days -28 to -2	Day -1	Day 1	Day 2	Day 3	Days 4 to 7	Day 8	Day 9	Day 10	Day 11 (EOS/ET)
Confined to the CRU		X	X	X	X	X	X	X	X	X
Outpatient Visit	X									
Inclusion/Exclusion Criteria	X	X								
Informed Consent	X									
Demographics	X									
Serology	X									
Medical History	X	Xa								
Height and BMI	X									
Weight	X	X								X^b
Drug Screen	X	X								
Alcohol Test		X								
Pregnancy Test (females only) ^c	X	X								X ^b
FSH (postmenopausal females only)	X									
12-lead Electrocardiogram ^d	X	X	X					X		X^b
Vital Signs ^e	X	X	X	X	X			X	X	X^{b}
Clinical Laboratory Evaluations ^f	X	X					X			X^{b}
eGFR ^g	X	X								
Thyroid-stimulating Hormone	X	X								X
Physical Examinationh	X	X								X^b
Sotorasib Dosei			X					X		
Omeprazole Dose ^j						X	X	X		
Sotorasib PK Blood Samples ^k			X	X	X			X	X	X
Adverse Event Monitoring ¹							X			
Serious Adverse Event Monitoring ¹	X					X				
Prior/Concomitant Medications ^m	X					X				

18 May 2022 Page 68 of 69

CONFIDENTIAL AMG 510 20220024

Abbreviations: BMI = body mass index; CRU = Clinical Research Unit; eGFR = estimated glomerular filtration rate; EOS = end of study; AT = early termination; FSH = follicle-stimulating hormone; PK = pharmacokinetic.

- ^a Interim medical history only.
- ^b Assessment to be performed at the EOS or ET.
- ^c Performed in serum at Screening and in urine at all other times. A positive urine pregnancy test will be confirmed with a serum pregnancy test.
- d Electrocardiograms (ECGs) will be collected after the subject has rested in the supine position for at least 5 minutes, and will be obtained prior to the scheduled blood draws. ECGs will be assessed at Screening, Check-in, at predose on Days 1 and 9, and at 0.5, 2, and 4 hours following sotorasib administration; and at EOS or ET. Triplicate ECGs will only be collected at Screening and Check-in if needed to verify eligibility criteria. The 30-minute postdose ECG measurement will have a collection window of \pm 5 minutes, the 2-hour postdose ECG measurement will have a collection window of \pm 10 minutes.

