- e Vital signs measurements (oral body temperature, respiratory rate, supine blood pressure, and supine heart rate) will be carried out, prior to having blood drawn, at Screening, Check-in, predose, and at 1, 24, and 48 hours after each dose of sotorasib, and at EOS or ET. Blood pressure and heart rate will be measured using the same arm for each reading after the subject has been resting in the supine position for at least 5 minutes.
- ^fClinical chemistry (fasted at least 8 hours), hematology, and urinalysis.
- g eGFR will be calculated using the Modification of Diet in Renal Disease equation.
- ^h A full physical examination at Screening and Check-in and a symptom-directed physical examination at EOS or ET.
- ¹ Dose administration of sotorasib is to occur during the mornings of Days 1 and 9 following an overnight fast of at least 10 hours. On Day 9, sotorasib administration will occur within 5 minutes after administration of omeprazole with an acidic beverage (Coca-Cola®).
- ^j Dose administration of omeprazole is to occur during the mornings of Days 4 through 9 following an overnight fast of at least 10 hours.
- k Blood samples for determination of sotorasib plasma concentrations and PK parameters will be collected: Predose (Hour 0), 0.5, 1, 1.5, 2, 3, 4, 6, 8, 10, 12, 24, 36, and 48 hours postdose following administration of sotorasib on Days 1 and 9. The PK sample collected 30 minutes postdose will have a sampling window of ± 2 minutes, samples collected from 1 through 3 hours postdose will have a sampling window of ± 5 minutes, samples collected from 4 through 10 hours postdose will have a sampling window of ± 10 minutes, and samples collected from 12 through 48 hours postdose will have a sampling window of ± 20 minutes. Times of all PK samples will be recorded to the nearest minute.
- ¹ Adverse events will be recorded from initiation of study treatment on Day 1 until EOS or ET. Serious adverse events will be recorded from the time the subject signs the Informed Consent Form through 30 days after the last dose of study treatment or until EOS or ET (whichever is later).

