6. STUDY TREATMENTS

The study treatment names, abbreviations, and ordering to be used in the TFLs are presented in [Table 1](#).

Table 1: Presentation of Study Treatments in TFLs

Study Treatment	Order in TFLs
Sotorasib administered alone	1
Omeprazole coadministered with Sotorasib and an acidic beverage	2

All TFLs will be based on actual treatments (eg, if subject was assigned to receive placebo but was wrongfully dosed with active treatment they would be summarized and listed under active treatment).

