8.6. Safety and Tolerability Assessments

8.6.1. Adverse Events

All AEs will be coded using the Medical Dictionary for Regulatory Activities (MedDRA) Version 25.0. (or higher if a new version is issued during the study; see the DMP for more details).

A treatment-emergent adverse event (TEAE) will be defined as an AE that starts during or after the first dose, or starts prior to the first dose and increases in severity after the first dose.

A treatment related TEAE will be defined as a TEAE with a relationship of possibly related or related to the study treatment, as determined by the investigator.

All AEs will be listed. In addition to the data recorded in the database, the listings will include derived onset time and duration. Onset time will be calculated from the time of dosing for TEAEs only.

The frequency of subjects with TEAEs and the number of TEAEs will be summarized for the following categories:

- TEAEs (overall, serious, leading to discontinuation, and leading to death) by treatment
- TEAEs by severity and treatment
- Treatment-related TEAEs (overall, serious, leading to discontinuation, and leading to death) by treatment
- Treatment-related TEAEs by severity and treatment

The frequency of subjects will be summarized separately for TEAEs and treatment-related TEAEs by the following:

- System organ class, preferred term, severity and treatment
- Preferred term, severity and treatment

For the AE data the following rules will apply:

- For the derivation of TEAE status: If the start date/time of an AE is incomplete or missing, an AE will be assumed to be a TEAE, unless the incomplete start date/time or the end date/time indicates an AE started prior to the first dose.
- For the derivation of treatment-related TEAE status: If the study treatment relationship for a TEAE is missing, a TEAE will be assumed to be a treatment-related TEAE.

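### By-treatment safety tables compare unequal observation: non-serious TEAEs over 72 h or more against about 48 h, serious TEAEs the reverse, and on the natural reading a QTcF maximum of 3 ECGs against 4

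*SAP*

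**What the plan says.** SAP Section 6, Table 1, gives two treatments for all tables: sotorasib alone and "Omeprazole coadministered with Sotorasib and an acidic beverage". Omeprazole alone on Days 4 to 8 has no column.

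**TEAEs.** SAP 8.6.1 plans "TEAEs (overall, serious, leading to discontinuation, and leading to death) by treatment", with further tables by severity, relatedness, system organ class and preferred term, all by treatment. Its rules on onset time and on repeated preferred terms presuppose that each event belongs to a treatment. They do not say how an event on Days 4 to 8 is assigned, when a treatment's window ends, or how unequal windows are handled. On collection, Protocol Appendix 8 says "Adverse events will be recorded from initiation of study treatment on Day 1 until EOS or ET". Serious events continue to 30 days after the last dose, or to end of study (EOS) if later (also Protocol 7.2.1).

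**QTcF.** SAP 8.6.4 says "The maximum postdose values will be summarized by treatment according to the following categories" and treats the maximum increase from baseline the same way. On the values used it says "The analysis will include all individual original, repeat, and unscheduled postdose values". Protocol Appendix 8 schedules ECGs at Screening and Check-in, then "at predose on Days 1 and 9, and at 0.5, 2, and 4 hours following sotorasib administration; and at EOS or ET". SAP 8.1.4 says "The baseline will be defined as the last value recorded prior to dosing" but does not say which dose is meant when there are two sotorasib doses.

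**The concern.** A column watched for longer collects more background events, and a maximum over more noisy readings is higher, even if the treatments are identical. Safety and tolerability of the combination is the secondary objective, and the SAP sets the two columns side by side. With 12 to 14 subjects, one or two extra subjects in a cell can change the impression. No planned table puts TEAEs on a common window. Rows of the same TEAE table (all events and serious events) also carry imbalances in opposite directions, so a reader cannot apply one mental correction.

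**Working it through.** The plan states no figure on this point and the sample size rests on precedent (SAP Section 5), so there is nothing to reproduce. The windows and counts come from the schedule. The incidences and SDs are assumptions, because the documents give none.

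**1. Observation windows.** Protocol Appendix 8 says "Dose administration of sotorasib is to occur during the mornings of Days 1 and 9". Omeprazole is given on the mornings of Days 4 to 9, and EOS is Day 11.

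- Sotorasib alone, up to the first omeprazole dose: Day 1 to Day 4 = 3 × 24 = 72 h.
- Sotorasib alone, if Days 4 to 8 are counted there: Day 1 to Day 9 = 8 × 24 = 192 h.
- Combination, non-serious events: Day 9 to Day 11 = about 48 h.
- Combination, serious events: 30 × 24 = 720 h.

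Non-serious ratio, sotorasib alone to combination: 72/48 = 1.5, or 192/48 = 4. Serious ratio, combination to sotorasib alone: 720/72 = 10, or 720/192 = 3.75.

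**2. Size for non-serious TEAEs.** Assume a constant hazard, the same in both columns. If a proportion r has an event within 48 h, the proportion within T hours is 1 − (1 − r)^(T/48). For r = 10%: 1 − 0.9^1.5 = 14.6% and 1 − 0.9^4 = 34.4%.

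| Assumed r (48 h) | 72 h | 192 h | Expected subjects of 14: 48 h / 72 h / 192 h |
|---|---|---|---|
| 5% | 7.4% | 18.5% | 0.7 / 1.0 / 2.6 |
| 10% | 14.6% | 34.4% | 1.4 / 2.0 / 4.8 |
| 20% | 28.4% | 59.0% | 2.8 / 4.0 / 8.3 |

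Setting Days 4 to 8 aside, the gap is 0.3 to 1.2 subjects. Counting them under sotorasib alone makes it 1.9 to 5.5. The larger range comes from the missing rule for Days 4 to 8.

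**3. ECG counts.** Three readings of the SAP are open:

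- EOS goes to the combination and Day 9 predose is a baseline: 3 against 4. This is the natural reading. The protocol labels the Day 9 reading predose, and EOS is a scheduled reading after dosing. SAP 8.1.2 generally excludes early-termination data, not EOS data.
- Baseline is taken before Day 1 only, and Day 9 predose counts as postdose for sotorasib alone: 4 against 4.
- EOS is left out of both columns: 3 against 3.

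**4. Size for QTcF at 3 against 4.** By simulation, the expected maximum of 3 independent standard normal readings is 0.847 and of 4 is 1.030, a shift of 0.18 within-subject SD. For an assumed SD of 5 to 10 ms that is 0.9 to 1.8 ms. At SD 10 ms with one shared baseline reading, the chance of an increase above 30 ms is 4.4% against 5.5%, or 14 × 0.011 = 0.15 of a subject. If each reading has chance p of crossing a category limit, the chance per subject is 1 − (1 − p)^3 against 1 − (1 − p)^4:

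| Assumed p | 3 ECGs | 4 ECGs | Expected subjects of 14 |
|---|---|---|---|
| 1% | 3.0% | 3.9% | 0.42 / 0.55 |
| 2% | 5.9% | 7.8% | 0.82 / 1.09 |
| 5% | 14.3% | 18.6% | 2.0 / 2.6 |

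The gap reaches about one subject (3.8 against 4.8) only at an assumed 10% per reading.

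**5. Would a 48 h window be fair?** It gives 48 h against 48 h, and the matched ECG times give 3 against 3. Laboratory tests are the exception. Appendix 8 schedules them at Screening, Day −1, Day 8 and Day 11. None falls within 48 h of the Day 1 dose, while the Day 11 test falls about 48 h after the Day 9 dose. An event dated by a laboratory test could therefore enter the combination column but hardly the other.

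**The case against.** The strongest reply is that little follows from this. SAP 8.6.6 plans no safety inference. The objective is to evaluate the coadministration and does not ask for a formal comparison with sotorasib alone. SAP 8.6.4 already provides ECG tables by timepoint and flags outlying values in the listings, and SAP 8.6.1 lists every AE with its onset time from dosing. The half-life of about 5 h (Protocol 1.2) means that the time beyond 48 h adds mainly background events. In a fixed-sequence design, equal windows would still leave period and order confounded with treatment. The table shells, a separate document, may settle the assignment.

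Most of this stands, and it limits the point to how the counts are read. It does not remove it. The timepoint tables help with QTcF, but no planned table does the same for TEAEs. Extra background events are exactly what separates two columns when there is no drug effect.

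Two further objections stand in full. The count of 3 against 4 ECGs is an inference, since the SAP assigns neither reading. A bare 48 h cut replacing the TEAE tables would bring in a bias for laboratory-detected events, among them raised liver enzymes, a named sotorasib risk (Protocol 1.4.1.2). It would also take late serious events out of the combination column.

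**Conclusion.** The SAP's two-column safety summaries rest on unequal observation without adjustment. For non-serious TEAEs the ratio is 1.5 (72 h against about 48 h), or 4 if Days 4 to 8 fall under sotorasib alone. With Days 4 to 8 set aside, the expected excess is roughly 0.3 to 1.2 subjects of 14 for assumed 48 h incidences of 5% to 20%. This is the main part of the point. The QTcF part is minor: 0.18 within-subject SD, and well under one subject in 14 for assumed crossing chances up to 5%.

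Three stronger conclusions that a reader might draw are not supported:

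- **That the TEAE tables favour the combination throughout.** For serious events its collection window is the longer one, 720 h against 72 to 192 h. This assumes that serious events after EOS enter the tables. SAP 8.1 ends the listings at study completion and is silent on the tables.
- **That the SAP prescribes 3 ECGs against 4.** It does not; 4 against 4 and 3 against 3 remain possible.
- **That a safety test is biased, or that the columns must differ.** No test is planned, and the difference is one of expectation.

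The sizes assume a constant hazard, independent readings and no drug effect.

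**What to change.** 1. **SAP 8.6.1.** Keep the full TEAE tables. Add a by-treatment summary of TEAEs, including serious ones, with onset within 48 h after each sotorasib dose. Tabulate separately the Day 4 to 8 events after omeprazole starts and the events after the 48 h window, so that none is lost. Show laboratory-detected events separately, with the reason (no laboratory test within 48 h of the Day 1 dose).
2. **SAP 8.6.4.** Base the by-treatment QTcF categories on the matched 0.5, 2 and 4 h readings of Days 1 and 9, with their repeats. Show EOS and unscheduled values in a separate row. State which predose reading is the baseline for each column.

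The cost is SAP and table-shell wording and a few extra rows in the safety tables. No new data are needed.
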